**5. Special precautions**

All collected information will be confidential and will not contain any identifying information. Surveys will be immediately placed in an opaque envelope by the researcher and stored in a locked cabinet. Electronic data compilation will be saved on a secure NorthShore Shared Drive.

**6. Experimental controls and use of placebos**

There will be two clinics that will not receive the initial round of OKQ trainings. After all surveys are collected, these clinics will be offered the opportunity to receive this training.

**7. Type and number of experimental subjects**

Up to 100 clinicians and staff that take part in the OKQ Training. Up to 234 patients from OB and FM clinics will be approached for to be surveyed.

**8. Statistical analysis**

A simple frequency and chi square analysis will be used to describe outcomes at each time point: baseline and post-OKQ.

To compare the effect of OKQ on preconception and contraceptive counseling, a difference-in-differences analysis will be conducted, comparing change in rate of counseling at the intervention practices vs. at the control practices.

**9. Potential risks and benefits**

The only risk includes loss of confidentiality if patients decide to share personal information while being verbally consented in the waiting room where other patients could overhear. However consenting will be done as privately as possible and patients will be encouraged to only provide the information necessary for the survey. All surveys are anonymous thus there should be not be a loss of confidentiality. There are no direct benefits to participants for participation.

**10. Monitoring of safety**

Patients will be asked during recruitment and consent whether they are able to safely participate in the study. Some questions could cause emotional distress due to the nature of the questions and if any adverse events occur during participation, the researcher will contact the patient's doctor, a counselor, or 911 (if necessary) and then report the event to the study PI and IRB as soon as possible.

**11. Payment**

A \$10 Walgreens or CVS gift card will be offered after participation to patients as a token of our appreciation and compensation for their time.

The clinicians and staff will not receive gift cards or other monetary incentives or compensations.

**12. Procedures to obtain and record informed consent**

- a. While in the waiting room, a researcher will approach a patient who appears to be 18-49, non-pregnant, and female after the patient checks in for her appointment.
- b. The researcher will read the oral recruitment and consent script. The patient has to agree to hear more about the study (after oral recruitment), provide verbal consent, and meet study criteria in order to participate. A one page information sheet (Appendix G) about the study and their rights

as a participant will be given while verbally consenting and if desired patients can take the one pager home to keep. See **Part II: Survey Collection** for more details on the overall recruitment and consenting process.

- c. An information sheet cover letter explaining the study (Appendix F) will be included in both the paper version and electronic version of the survey provided to clinicians and staff. The cover letter will be in the body of the email which contains the link to the survey. The link will be listed after the cover letter. Please see section **Part II: Survey Collection subsection c** for more information.

### **13. Confidentiality**

No identifying information will be collected during consent or study participation. Participants will be asked to place completed surveys in an opaque envelope before handing over the survey to the RA. At the end of the collection day, the surveys will be stored in a locked unit. All electronic information will be secured on a NorthShore encrypted server.

### **15. Recruiting methods**

- a. RA will approach female patients in waiting room that appear to be w/in study age range and not pregnant

- b. The RA will ask (following the oral recruitment/consent script) if the patient would like to participate in the study
- c. The patient will be seen by the provider
- d. The patient will then return and approach the RA to complete the survey
- e. As for clinician and staff recruitment, research staff will attend clinic staff meetings at intervention practices to introduce the survey in-person in order to increase buy-in among respondents. For more details see section **Part II: Survey Collection subsection c.2.**

**16. How the subject's primary physician will be notified**

The participant's physician will not be notified if the she has consented to participate.

**17. Anticipated coordination between inter-departmental faculty**

We will schedule a meeting at the beginning and end of this study phase to ensure that OB and FM offices know the status of this study.

**18. Rational for excluding women, minorities, and/or children from participation**

Pregnant women and children are excluded from participation because the care they receive will not provide the data we need for this study's objectives.

One Key Question: Pilot Study at NorthShore

Statistical Analysis Plan

Clinicaltrials.gov (NCT03947788)

11/17/2020

Patients were excluded from analysis if they reported experiencing menopause or having a hysterectomy or sterilization. Since OKQ is a practice-level intervention, we used intention-to-treat analysis and calculated each practice's rate for each outcome, regardless of whether patients' individual physician had participated in the OKQ training. In each group of patients (baseline time point in control and intervention practices, and post-intervention time point in control and intervention practices), we calculated the percentage receiving reproductive counseling and the percentage who were extremely or very satisfied.

We used chi square tests to compare rates across the two time points within each practice. We also used multivariable logistic regression with an intervention time point interaction (difference-in-differences) term to assess intervention efficacy independent of differences across sites and time trends unrelated to the intervention, controlling for practice type (ob/gyn vs. primary care), patient age, race/ethnicity, and reason for visit. Results are reported as adjusted odds ratios (aOR) and 95% confidence intervals (CI). All analyses were conducted using SAS 9.4 (SAS Inc., Cary, NC).

We calculated a minimum sample size of 260 was needed to observe a 15% between-group difference in the pre-to-post change in counseling rates with 80% power. The statistical significance level for all tests was <0.05.

This research was registered on clinicaltrials.gov (NCT03947788) and approved by NSUHS Institutional Review Board (IRB). Analysis of de-identified data was exempted by the University of Chicago IRB (The University of Chicago, 19-0149; NSUHS, 18-343).

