### **1. Background**

Effectively delivered preconception counseling leads to healthier pregnancy behaviors (1), and high quality contraceptive counseling leads to more effective birth control use (2-4), both of which improve outcomes for women and their offspring (5-7). The Centers for Disease Control and Prevention (CDC) recommend that primary care and reproductive health providers routinely ask reproductive age patients about their personal goals regarding pregnancy and offer preconception and contraceptive counseling guided by the patient's preferences (8). However, only 14% of ambulatory visits by reproductive age women in the United States include any preconception or contraceptive counseling (9). Many clinicians miss opportunities to provide this counseling because they lack tools to identify women who would benefit from it, and may not have the care processes in place to provide appropriate counseling and access to evidence-based care once the need is identified. This need is addressed through our intervention: the One Key Question® (OKQ), a program run through the nonprofit *Power To Decide* to help clinicians efficiently address women's pregnancy intention and provide evidence-based care (Appendix A). Clinicians are trained to ask patients, "Would you like to become pregnant in the next year?" and address contraception and preconception health in a supportive, patient-centered manner. The program provides clinician and staff training, evidence-based clinical tools, and efficient workflows to implement the CDC recommendations (10, 11). We have collected baseline needs assessment data by surveying patients at 6 obstetrics and gynecology and family medicine groups within Northshore University Health Systems (EH 18-015). All 6 of these clinics (see page 3) have agreed to participate in future trainings and post-intervention survey collection at their sites.

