### **3. Methodology**

#### **Part I: Trainings**

- a. 2 of the 4 participating NorthShore Medical Groups will be selected to receive *Power To Decide* OKQ trainings. These become the *intervention practices* and the remaining 2 become *control practices*. The selection of these sites will be determined based on site availability, willingness to participate, and clinic characteristics.
- b. Trainings will be provided to clinicians and staff from the intervention practices.
- c. Trainers from *Power To Decide* will execute OKQ trainings
- d. Trainings consist of:
  - Up to seven hours of training, in-person certification training (Appendix B)
  - Provider and Patient Materials
  - Five hours of consulting (prior to and following training)
  - Post training webinar
  - Provider OKQ Certification (two years for the price of one)
  - Access to a OKQ Provider Portal (only available to certified providers)

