### **Part II: Survey Collection – Starts at least 4 weeks after OKQ Training**

- a. The research team will work with physicians and practice managers at all participating NorthShore practices to select mutually agreeable days for data collection at each site.
- b. On data collection days, patient surveys will proceed using the same procedures as those used for baseline data (EH 18-015). Specifically:
  1. A research assistant (RA) will approach a patient in the waiting room before her appointment. After verbal recruitment and consent, the RA will determine if she qualifies for the study.
  2. If the patient is eligible, the RA will explain the study and ask that she comes back to the waiting room after her appointment to fill out a post-exam survey. The RA will instruct the participant to place completed survey in an envelope.
  3. The RA will collect the survey and offer a \$10 Walgreens or CVS gift card as a token of appreciation for participating in the study.
- c. After patient data collection is complete, the RA will return to each practice to collect surveys from clinicians and staff (Appendix C) at the intervention practices to assess the experience of implementing OKQ and their perceptions of its utility for patients.
  1. OKQ staff will attend clinic staff meetings at intervention practices to introduce the survey in-person in order to increase buy-in among respondents.
  2. Clinicians and staff will receive the survey through an emailed link as well as in paper form:
    - i. A paper survey with a cover letter (Appendix F) attached will act as our consenting process. This cover letter will also include a link to the online version of the survey if they choose to complete the survey online.
    - ii. All clinician and staff will receive an email that includes a copy of the cover letter and a link to the survey online.
  3. All individuals taking these surveys on paper forms will be asked to leave their completed surveys at their clinic in a secure location for the RA to pick up.

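### The SAP's four arm-by-wave percentages weight each practice by its survey count, which the documents do not fix, so a shift in practice mix between waves could look like a change in counseling

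*SAP*

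**What the plan says.** The SAP's first paragraph defines four cells, "In each group of patients (baseline time point in control and intervention practices, and post-intervention time point in control and intervention practices", and for these "we calculated the percentage receiving reproductive counseling and the percentage who were extremely or very satisfied". I read this as one percentage over all women in the cell. The same paragraph also has each practice's own rate calculated for each outcome.

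The SAP's second paragraph adds chi-square tests between waves inside each practice. It also specifies a logistic difference-in-differences model "controlling for practice type (ob/gyn vs. primary care), patient age, race/ethnicity, and reason for visit", reported as adjusted odds ratios. The stated aim of that model is to separate the intervention effect from site differences and time trends. It has no practice identifier.

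The protocol supplies the rest:

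- **Practices per arm** (Section 3, Part I): "2 of the 4 participating NorthShore Medical Groups will be selected to receive" the training; the other two are controls.
- **Number of patients** (Section 7): "Up to 234 patients from OB and FM clinics will be approached for to be surveyed". There is no split by practice or arm.
- **Survey days** (Section 3, Part II): the team works with the practices "to select mutually agreeable days for data collection at each site".
- **Baseline** (Section 1): already collected under EH 18-015 by "surveying patients at 6 obstetrics and gynecology and family medicine groups". Counts per practice are not given.
- **Difference-in-differences** (Section 8): "comparing change in rate of counseling at the intervention practices vs. at the control practices". No weighting or covariates are named.

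**The concern.** A percentage over all women in an arm is an average of its two practice rates, weighted by how many women each practice contributed. The two waves were collected separately, on days agreed site by site, so nothing in the available text holds those weights constant. If one practice counsels more often than the other and its share of surveys rises, the arm's percentage rises although neither practice has changed. The movement can go either way, so it could create an apparent effect or hide a real one. More surveys at the same mix would not cure it.

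At stake is the comparison a reader makes by subtracting the four percentages, and the Section 8 comparison if it is built from them. To a lesser degree it also affects how far the adjusted odds ratio is free of site differences, as the SAP intends.

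**Working it through.** **1. The benchmark.** The SAP's third paragraph gives a minimum of 260 for a 15% between-group difference in change, with 80% power and a 0.05 significance level. I read 15% as percentage points and the test as two-sided. A two-group comparison of 14% with 29% gives 234 in total without continuity correction and 260 with it. The 14% is the national figure in protocol Section 1, which the SAP does not declare as its planning rate. The match makes 15 points a fair yardstick; nothing below depends on it.

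**2. Formula.** Let an arm have practices A and B with unchanged rates pA and pB, and let A supply a share w of the arm's surveys.

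- Cell percentage = w·pA + (1 − w)·pB
- Change between waves = (w_post − w_base) × (pA − pB)

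**3. Range.** The documents give no practice rates or shares, so these inputs are assumptions. The table shows the spurious change in points if only one arm's mix moves.

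| Gap in rates (points) | Share shift 10 | Share shift 20 | Share shift 30 |
|---|---|---|---|
| 10 | 1 | 2 | 3 |
| 20 | 2 | 4 | 6 |
| 30 | 3 | 6 | 9 |
| 40 | 4 | 8 | 12 |

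If either the gap or the shift is zero, the change is zero. If the other arm moves equally in the opposite direction, each entry doubles, giving 2 to 24 points.

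**4. Worked case.** Assume practices at 60% and 30% in both arms, and no change in care.

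- Baseline, 50:50 in both arms: 0.5 × 60 + 0.5 × 30 = 45%.
- Intervention arm moves to 70:30: 0.7 × 60 + 0.3 × 30 = 51%. Control stays at 45%. Spurious difference: 6 points, or 6/15 = 40% of the design effect. Unadjusted interaction odds ratio: (0.51/0.49)/(0.45/0.55) = 1.27.
- Control also moves, to 30:70: 0.3 × 60 + 0.7 × 30 = 39%. Spurious difference: 51 − 39 = 12 points, or 12/15 = 80%. Odds ratio: (0.51/0.49)/(0.39/0.61) = 1.63.

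**5. The adjusted odds ratio.** I fitted the logistic model to expected counts with arm, wave, their interaction and practice type, leaving out the patient-level covariates. The true interaction odds ratio is 1.00 throughout, and only the intervention mix moves (50:50 to 70:30).

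| Layout (assumed) | Adjusted for practice type | Adjusted for practice |
|---|---|---|
| One ob/gyn and one primary care practice per arm, 60/30 in both arms | 1.00 | 1.00 |
| Same layout, 60/30 in intervention, 50/40 in control | 1.09 | 1.00 |
| Two ob/gyn in intervention, one of each in control, 60/30 in both arms | 1.27 | 1.00 |
| Two ob/gyn in intervention, two primary care in control, 60/30 in both arms | not estimable (type coincides with arm) | 1.00 |

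**6. After the fix.** With fixed 50:50 weights in both waves, every cell in the worked case is 45% and the difference-in-differences is 0.

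**The case against.** Most of the case on the other side stands as a limit on the point.

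- **The efficacy result is the adjusted odds ratio.** A reader might infer that the four percentages are the trial's main result. The SAP does not support that: it assesses efficacy through the interaction term, and the percentages are descriptive.
- **The SAP already contains results that mix cannot disturb.** The practice-specific rates and within-practice chi-square tests would expose a pooled percentage that moved while both practices stayed flat. They do not, however, correct the pooled figure or give a contrast between arms.
- **Section 8 is silent, not unadjusted.** A reader might infer that the protocol commits to an unadjusted pooled difference-in-differences. It names no covariates, but it does not rule them out, and the later SAP specifies an adjusted regression. The point reaches Section 8 only if its rates are the pooled ones.
- **No bias is shown.** A reader might infer that the reported percentages are wrong. The documents give no practice rates, no survey shares and no evidence of a shift.
- **A target may exist elsewhere.** The available text lacks the part of the protocol between Section 3, Part II and Section 5, and the baseline protocol is not supplied. A number per practice there cannot be excluded, although Section 7, the natural place for it, gives only a total.
- **Practice type may be enough.** With one practice of each type per arm, it removes most or all of the problem from the odds ratio, and patient covariates may absorb more. The documents do not give types by arm. Part I lists site availability, willingness and clinic characteristics as selection criteria, which does not guarantee that layout.

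A percentage weighted by patients is a legitimate description of one cell. It becomes unsafe when cells with different mixes are subtracted.

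**Conclusion.** The point holds as a vulnerability. The four percentages, and any rate comparison drawn from them, are open to changes in practice mix that nothing in the available text controls. Size: 1 to 12 points if one arm's mix moves, over the assumed gaps and shifts, against a 15-point design effect; nil if the practices have similar rates or a stable mix. For the adjusted odds ratio, exposure ranges from none to the full unadjusted distortion (1.27 in the worked case), depending on how practice types fall across arms. The conclusion assumes two practices per arm and that the SAP's percentages pool women within each cell. It does not extend to the practice-specific rates or the within-practice tests.

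**What to change.** 1. **Protocol Section 7, if collection is still open:** allocate post-training surveys across practices in the same proportions as each practice's baseline surveys. The SAP is dated 11/17/2020 and written in the past tense, so this may come too late. The cost is less freedom in scheduling survey days.
2. **SAP, first paragraph:** compute each arm-by-wave percentage as a mean of the practice rates, using one fixed set of weights within each arm (baseline shares) in both waves. Derive any rate difference-in-differences from these. The practice rates are already calculated, and with baseline shares the baseline percentages stay as they are. The cost is a slightly larger standard error. In the worked case (n surveys at 70:30, weights 50:50) the variance is (0.25 × 0.24/0.7 + 0.25 × 0.21/0.3)/n = 0.261/n, against (0.7 × 0.24 + 0.3 × 0.21)/n = 0.231/n for the pooled figure. The standard error is √(0.261/0.231) = 1.06 times as large.
3. **SAP, second paragraph:** replace practice type with practice indicators, so that the odds ratio is free of stable site differences as the SAP intends. With four practices, two within-arm indicators take the place of one type term, a net cost of one parameter and possibly some precision.

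Step 2 needs one SAP sentence and step 3 a change of covariate. Both can be applied to data already collected, provided the practice is recorded for each survey, as the within-practice tests require.

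### Satisfaction is analysed only as top two levels versus the rest, which hides shifts on either side of the cut and loses precision by an amount the documents do not let us fix

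*SAP*

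**What the plan says.** The SAP has two patient outcomes. For each of the four groups (control and intervention practices, at baseline and post-intervention), it calculates the share given reproductive counseling and "the percentage who were extremely or very satisfied". It then gives two analyses:

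- Unadjusted: "We used chi square tests to compare rates across the two time points within each practice".
- Adjusted: "multivariable logistic regression with an intervention time point interaction (difference-in-differences) term", controlling for practice type, age, race/ethnicity and reason for visit. Results are given as adjusted odds ratios with 95% intervals.

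The regression sentence names no outcome; I read it as covering both. The SAP mentions no ordinal model, no table of the full ratings and no reason for the cut point. It does not state the number of response levels or any expected or baseline distribution. The only design figure concerns the other outcome: a "minimum sample size of 260 was needed to observe a 15% between-group difference in the pre-to-post change in counseling rates with 80% power". The protocol text supplied does not mention satisfaction, and its section 8 (Statistical analysis) applies the difference-in-differences comparison to counseling only.

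**The concern.** Two different satisfaction labels are named on one side of the cut, so the item is ordered and has at least three levels. Reducing it to two has two separate consequences.

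1. **Movement that leaves the cut uncrossed is invisible.** A patient group that shifts from *very* to *extremely*, or the reverse, or among the lower levels, shows no change in the planned percentage and an odds ratio of 1. A null result could then be read as no effect on satisfaction although the ratings had moved.
2. **Precision is lost even when the cut is crossed.** If the whole distribution shifts, the binary model still estimates the shift, but with a wider interval than the full scale would give.

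The second matters here because the sample size was set on counseling, so satisfaction has no power provision of its own.

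**Working it through.** **Plan's own figure.** There is none to reproduce. The SAP states neither an expected satisfaction rate nor a power calculation for it.

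**Hidden movement.** Take hypothetical ratings of 50/30/15/4/1 per cent, from *extremely* downwards, moving to 40/40/15/4/1. The top-two share is 80% both times, so the binary odds ratio is 1. The odds of *extremely* go from 0.50/0.50 = 1.00 to 0.40/0.60 = 0.67. The planned analysis cannot register this.

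**Lost precision.** Let p be the top-two share and p_i the share at each level. For small effects under proportional odds, with independent patients and similar distributions in the four cells, the information kept by the binary cut relative to the full scale is

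RE = 3p(1 − p) / (1 − Σ p_i³), and the loss is 1 − RE.

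The documents give neither p nor p_i, so every distribution below is an assumption (five levels).

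| Assumed levels (%) | Top two | 3p(1 − p) | 1 − Σ p_i³ | RE | Loss |
|---|---|---|---|---|---|
| 5/45/45/4/1 | 50% | 0.750 | 0.818 | 0.92 | 8% |
| 20/30/30/15/5 | 50% | 0.750 | 0.935 | 0.80 | 20% |
| 40/30/20/7/3 | 70% | 0.630 | 0.901 | 0.70 | 30% |
| 50/30/15/4/1 | 80% | 0.480 | 0.845 | 0.57 | 43% |
| 60/30/7/2/1 | 90% | 0.270 | 0.757 | 0.36 | 64% |
| 60/35/3/1/1 | 95% | 0.1425 | 0.741 | 0.19 | 81% |

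Next, hold the top-two share fixed and vary the split within it from 10:90 to 90:10, dividing the remainder 70:20:10 among the lower three levels. The last column is the factor by which the interval on the log-odds scale is widened, 1/√(1 − loss).

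| Top-two share | Loss | Interval width factor |
|---|---|---|
| 50% | 13–19% | 1.07–1.11 |
| 60% | 12–22% | 1.07–1.13 |
| 70% | 15–30% | 1.08–1.20 |
| 80% | 23–45% | 1.14–1.35 |
| 90% | 42–67% | 1.31–1.74 |
| 95% | 62–82% | 1.62–2.36 |

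These ranges are not hard limits. The 8% in the first table lies below the 50% row because its lower levels are divided differently, and 5/75/15/4/1 (top two 80%) gives 16.5% because its top split is more extreme than 10:90.

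**Does the assumed number of levels matter?** Little, in the cases tried. With everything below the cut merged into one level:

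- 50/35/15: 0.3825/0.829 = 0.46, against 0.46 for 50/35/10/3/2.
- 40/40/20: 0.480/0.864 = 0.56, against 0.55 for 40/40/13/5/2.
- 30/40/30: 0.630/0.882 = 0.71, against 0.70 for 30/40/20/7/3.

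In these examples nearly all the loss comes from merging the top two levels.

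**The case against.** The case against acting is fair on several counts.

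- **The estimand is legitimate.** A top-two percentage is easy to read and the cut does not bias it. Satisfaction is not the outcome used for the sample size, so the pilot's main inference is untouched. This stands, and it limits the weight of the point.
- **The two consequences need different models.** Under proportional odds a shift appears at every cut with the same odds ratio, so the binary model loses only precision. Movement confined to the top two levels violates proportional odds, and the loss figures then do not apply. This also stands. It is why the remedy needs the full distribution as well as the ordinal model.
- **Patients are not independent.** The protocol has two intervention and two control practices (sections 2 and 3). Practice-by-period variation is not removed by finer scoring of each patient, so the real gain would be smaller than the tables show.
- **It is late.** The SAP is dated 11/17/2020 and written in the past tense, so replacing the model would be a post hoc change. This argues for an added analysis, not against one.

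A reader might go further and infer three things that the documents do not support. The first is a fixed loss, say a third to a half of the information; that follows only for some distributions, and none is reported. The second is that ratings sit near the ceiling; no satisfaction figures are given. The third is that the cut conceals harm from an unwelcome question. Nothing in the SAP suggests this, and a fall from the top two levels to a lower one is exactly what the cut would detect.

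**Conclusion.** The point holds in a limited form. The SAP collapses an ordered rating to two classes without giving a reason and names no analysis of the full scale. It is therefore blind to shifts within either class and gives up precision on one of two patient outcomes. The percentage it reports is unbiased.

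Every distribution tried showed some loss, from about 8% to 82%. On the grid used, the loss is 12–30% for a top-two share of 50–70%, 23–45% at 80%, and 42% or more at 90% or above. These figures rest on five assumed levels, independent patients, small effects and proportional odds, and they overstate the practical gain if practices vary over time. This is a cheap improvement to a secondary matter, not a flaw in the main comparison.

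**What to change.** 1. Add a proportional-odds (cumulative logit) model of the full satisfaction rating, with the same intervention-by-time term and the same covariates. Label it as an added analysis, because the SAP describes the analyses as already done.
2. Tabulate the full response distribution in each of the four group-by-time cells, and state the number of levels and their wording. This table shows movement within the top two levels whether or not proportional odds holds.
3. Keep the top-two percentage and its binary adjusted odds ratio.
4. Check proportional odds, for example by comparing the interaction odds ratio across cut points. If it fails, the binary result and the full distribution stand. If the lowest levels are sparse, merge them and say so; in the examples above that cost almost nothing.

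The cost is one further model and one table in software already in use, from ratings already needed to compute the percentage. The downside is reliance on proportional odds, which a small pilot can check only roughly.

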### **2. Purpose**

The purpose of this pilot study is to build upon baseline data on pregnancy intention and receipt of contraceptive and preconception counseling. 2 of the 4 participating practices will be randomly selected to receive comprehensive One Key Question® training through the nonprofit *Power To Decide*. All trained sites also have access to technical support in implementing OKQ. This training and technical support will act as the intervention and be given to help improve the quality of preconception and contraceptive counseling in Primary care and Obstetrics/Gynecology. All participating practices will then be surveyed again to determine changes in contraception and preconception counseling. Following this second round of surveys, the remaining practices will have the option to receive *Power To Decide*'s One Key Question ® training.

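### OKQ is allocated to four practices, two per arm, but the SAP tests it as if patients were independent, so its P value is too small and its interval too narrow if practices drift differently.

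*SAP*

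**What the plan says.** On allocation, Protocol section 2 (Purpose) says "2 of the 4 participating practices will be randomly selected" for training. Section 3, Part I also has two intervention and two control practices, and section 6 confirms two clinics without the initial training. The SAP acknowledges the level of allocation: "Since OKQ is a practice-level intervention, we used intention-to-treat analysis".

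On analysis, Protocol section 8 plans a difference-in-differences comparison and names no method for clustering. The SAP puts this into a patient-level model: "We also used multivariable logistic regression with an intervention time point interaction (difference-in-differences) term to assess intervention efficacy". It says that the result is "independent of differences across sites and time trends unrelated to the intervention". The covariates are type of practice and patient age, race/ethnicity and visit reason; significance is judged at 0.05. The SAP also calculates a rate for each practice and runs chi-square tests between waves within each practice.

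On size, the SAP states: "We calculated a minimum sample size of 260 was needed to observe a 15% between-group difference". It gives no intracluster correlation or design effect, and does not say whether 260 is a total or a number per wave. Protocol section 7 says: "Up to 234 patients from OB and FM clinics will be approached".

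**The concern.** The between-arm contrast rests on four changes, two per arm. A patient-level logistic model without a cluster term takes its standard error from the number of patients, not the number of practices.

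Difference-in-differences removes stable differences between practices and any time trend that both arms share. It does not remove a change that occurs in one practice and not in the others, such as staff turnover or a local initiative, unless the patient covariates explain it. With two practices per arm, such a change makes up half of that arm's estimated change and can look like an OKQ effect. The SAP's statement about time trends therefore claims more than the model delivers, and the 5% level behind its efficacy statement is not assured.

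Type of practice, the only site-level covariate, is not an allowance for clustering. The within-practice rates and tests do not enter the standard error of the interaction.

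**Working it through.** **The plan's own figure.** A two-group comparison of 14% with 29% (two-sided 0.05, 80% power, continuity-corrected) needs 130 per group, 260 in total. Without the correction it is 117 per group, or 234, the number in Protocol section 7. The 14% is assumed: it is the national rate in Protocol section 1 and the only rate in the documents. The same inputs in a four-cell difference-in-differences need (1.96 + 0.84)² × (3 × 0.14 × 0.86 + 0.29 × 0.71) / 0.15² = 198 per cell, 792 in total. The match suggests, but does not prove, that planning used a patient-level two-group formula with no design effect.

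**Inputs.** Four practices, two per arm, two waves. Patients per practice per wave (n): about 33 if 260 is the total (260/8), or 65 if it is per wave (260/4; 520 in all). The 234 patients in Protocol section 7, if they are the post-training wave only, would be at most about 58 per practice. Counseling rate (p): 14%, or 40% as an assumed higher value. Practice-by-wave SD on the logit scale after covariate adjustment (s): not in the documents, assumed 0 to 0.4. An SD of 0.2 corresponds to a latent intracluster correlation of 0.04 / (0.04 + π²/3) = 0.012.

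**Formula.** Each practice-by-wave log odds has sampling variance 1/[n p(1−p)] plus s². The interaction combines eight of these, each with weight ½, so its variance is 2 × {1/[n p(1−p)] + s²}. A patient-level model counts only the first part. The interval should therefore be wider by √[1 + s² n p(1−p)]:

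- s = 0.2: √(1 + 0.04 × 33 × 0.1204) = 1.08, up to √(1 + 0.04 × 65 × 0.24) = 1.27.
- s = 0.4: √(1 + 0.16 × 33 × 0.1204) = 1.28, up to √(1 + 0.16 × 65 × 0.24) = 1.87.

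**Simulation.** 4,000 trials per setting with no true effect, one practice of each type per arm, a stable practice SD of 0.3, simulated patient covariates, and the SAP's model without a cluster term. False-positive rate of the nominal 5% test:

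| n per practice per wave | p | s = 0 | 0.1 | 0.2 | 0.3 | 0.4 |
|---|---|---|---|---|---|---|
| 33 | 14% | 5.1% | 5.9% | 6.6% | 8.3% | 12.5% |
| 33 | 40% | 5.4% | 5.7% | 9.0% | 12.7% | 18.1% |
| 65 | 14% | 4.4% | 6.1% | 8.9% | 13.7% | 19.5% |
| 65 | 40% | 4.7% | 6.6% | 12.1% | 19.9% | 27.7% |

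The formula agrees. For n = 33, p = 14%, s = 0.4, it gives 2 × [1 − Φ(1.96/1.28)] = 12.5%.

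**Alternatives.**

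- Practice fixed effects: 28.1% against 27.7% in the worst setting, so no help.
- Uncorrected cluster-robust errors: about 30% at every s, so worse.
- A t test on the four unadjusted practice changes (2 degrees of freedom): about 4–5% throughout, on the rate or the logit scale.

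**Price of the practice-level interval.** With every arm-by-wave cell at 14% and no clustering:

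- 65 per cell (260 in all): SE = √(4 × 0.14 × 0.86 / 65) = 0.0861. The half-width goes from 1.96 × SE = 16.9 points to 4.30 × SE = 37.0 points.
- 130 per cell (520 in all): SE = 0.0609, and the half-width goes from 11.9 to 26.2 points.

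Power for a 15-point effect from 14%, without clustering, falls from 36% to 16% (260 in all) or from 62% to 26% (520).

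**The case against.** The strongest reply is that the harm is conditional. At s of 0 to 0.1 the test runs at about 4–7%, close to nominal, and the highest rates need both s = 0.4 and the 520-patient reading. That stands, and the size cannot be fixed from the documents.

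The SAP is also a short summary. Independence of patients is inferred from its silence, and stating the variance method that was used would settle the point. It already calculates practice rates, so drift in one practice would be visible to a careful reader. That deserves credit, but those rates do not alter the interval or P value offered as evidence of efficacy.

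This is a pilot, which argues for an exploratory label rather than against the point.

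On the count of practices, Protocol section 1 says that six clinics agreed to take part, and the SAP gives no number. Sections 2, 3 and 6 support four. Three per arm would give 4 degrees of freedom and a critical value of 2.78. One practice of each type per arm is a simulation assumption. The 2-degree-of-freedom test was checked on unadjusted changes only, not on covariate-adjusted ones.

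**Conclusion.** The concern holds. OKQ is allocated by practice, and the only between-arm efficacy test names no allowance for this. Stable practice differences are not the problem; different changes between waves are. The false-positive rate is about 5% without such changes, 7–12% at a logit SD of 0.2 and 13–28% at 0.4, and the interval should be 1.1–1.3 and 1.3–1.9 times as wide. These sizes rest on an assumed SD, on counseling rates of 14% to 40%, on both readings of 260, and on a model without a cluster term. That the nominal level is not assured rests only on the allocation to four practices and the absence of a named cluster method. It must be fixed, because it affects the main inferential result.

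**What to change.** In the SAP's analysis paragraph:

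1. State the number of practices per arm and the variance method used for the interaction.
2. Report the four pre-to-post changes, unadjusted and covariate-adjusted, and the intervention-minus-control difference with an interval that uses the practice as the unit. With two practices per arm this is the difference in mean change ± 4.30 × √[(v₁ + v₀)/2], where v₁ and v₀ are the within-arm variances of the changes. Name the scale: percentage points match the sample-size statement, and log odds match the adjusted odds ratio.
3. Label the patient-level odds ratio and interval as reflecting patient sampling error only.
4. Replace the efficacy wording with exploratory pilot estimation, and limit the statement on time trends to trends shared by both arms.
5. Do not rely on practice fixed effects, or on sandwich or GEE errors alone, with four practices.

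A permutation test is no substitute: with two of four practices its smallest two-sided P value is 1/3. It would also need random allocation, on which the protocol conflicts. Section 2 says "2 of the 4 participating practices will be randomly selected", while section 3, Part I says "The selection of these sites will be determined based on site availability, willingness to participate, and clinic characteristics". These should be reconciled as a separate matter.

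The cost is SAP wording and a few lines of code, with no new data, since practice rates are already calculated. The interval becomes much wider and, with 16–26% power, serves for estimation rather than for a verdict on OKQ.
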